### 3.2.1 Screen Failure

A screen failure is defined as a subject who has signed the ICF, does not meet all the entry criteria outlined in [Section 4.3](#) of this protocol (note that this includes assessments prior to receiving treatment on Visit 1) and was not randomized to receive study treatment (active or placebo). The Investigator is responsible for keeping a record of all subjects screened for entry into the study and subsequently excluded. The reason(s) for exclusion will be recorded in the source documents and on the Screening log. Screen failure subjects will have only their consent, demographic and reason for screen failing (including, where applicable, the unmet inclusionary or exclusionary criteria) data entered into the electronic data capture (EDC) system, unless an adverse event was responsible for

the subject's screen failure, in which case all data collected for that subject during the screening process will be entered into the EDC system.

### **3.3 Treatment Period**

The Treatment Period will last for 4 weeks from Visit 1 (Day 0) to Visit 3 (Day 28).

#### **3.3.1 Visit 1 (Week 0, Day 0)**

Subjects will report to the clinic in morning following a 10-hour fast. At Visit 1, the following procedures will be performed:

- Review of inclusion and exclusion criteria;
- Review of prior and current medications and supplements;
- Measurement of vital signs (SBP/DBP and heart rate);
- Measurement of weight;
- Breathalyzer;
- Subjects will be randomized to either ORMD-0801 (8 mg) or placebo. Subjects will be instructed to dose twice a day. Doses will occur at 45 minutes ( $\pm$  15 minutes) before breakfast and no later than 10 AM each morning, and at bedtime (@ 8 PM  $\pm$  120 minutes) each night, and no sooner than 1 hour after dinner;
- Study medication will be dispensed;
- Blood sample will be collected to measure HbA1c;
- AEs/SAEs assessment;
- Remind subjects to arrive fasting for Visit 2 in 2 weeks.

#### **3.3.2 Visit 2 (Week 2, Day 14)**

Subjects will report to the clinic in morning following a 10-hour fast. At Visit 2, the following procedures will be performed:

- Review of prior and current medications and supplements;
- Measurement of vital signs (SBP/DBP and heart rate);
- Measurement of weight;
- Breathalyzer;
- Study medication will be collected, and compliance will be reviewed;
- Study medication will be dispensed;
- Blood sample will be collected to measure HbA1c;
- AEs/SAEs assessment;
- Remind subjects to arrive fasting for Visit 3 in 2 weeks.

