Secondary Objectives: 

1. To compare the change from baseline in HbA1c levels measured at Week 4 in type 2 diabetic patients treated for 4 weeks with either ORMD-0801 or matching placebo.

2. To compare the change from baseline in plasma glucose levels measured at Week 4 in type 2 diabetic patients treated for 4 weeks with either ORMD-0801 or matching placebo.

3. To compare the change from baseline in ketone levels measured at Week 4 in type 2 diabetics treated for 4 weeks with either ORMD-0801 or matching placebo.

4. To compare the change from baseline in FFAs measured at Week 4 in type 2 diabetics treated for 4 weeks with either ORMD-0801 or matching placebo.

5. To compare the change from baseline in TC, LDLC, HDLC, and TG measured at Week 4 in type 2 diabetics treated for 4 weeks with either ORMD-0801 or matching placebo.

6. To assess the differences in endogenous glucose production in patients with type 2 diabetes treated for 4 weeks either with ORMD-0801 or matching placebo following an intravenous infusion of [6,6-2H2]-glucose tracer using other parameters including, but not limited to, Cmax, Tmax, Tlag and AUC over different time intervals.

7. To assess the safety of repeat administration of ORMD-0801 in patients with type 2 diabetes inadequately controlled on oral therapy.

	Secondary Endpoints: 

1. Mean changes in HbA1c from baseline to Day 29 of the treatment period.

2. Mean changes plasma glucose levels from baseline to Day 29 of the treatment period.

3. Mean changes in ketones from baseline to Day 29 of the treatment period.

4. Mean Changes in FFA from baseline to Day 29 of the treatment period.

5. Mean change in TC, LDLC, HDLC and TG from baseline to Day 29 of the treatment period.

6a. Difference in endogenous glucose production between active and placebo as measured by the glucose with tracer attached using other parameters including, but not limited to:

a. AUC(0-2), AUC(0-4), AUC(0-8), AUC(0-12),

b. AUC(2-16), AUC(4-16), AUC(8-16), AUC(12-16),

c. Cmax,

d. Tmax, and

e. Tlag.

6b. Difference in metabolites (β-hydroxybutyrate, acetoacetate, lactate, pyruvate, FFA, glycerol) and hormones (insulin, C-peptide, glucagon) between active and placebo using the same AUC intervals as endogenous glucose production.

7. Safety assessed by adverse event reporting including adverse events of special significance such as hypoglycemia.

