### **3.6 Early Withdrawal (EW)**

If a randomized subject is withdrawn from the study prior to completion, the subject will be instructed to return to the clinic the next day and will have the early term (ET) visit procedures completed. Subjects will then be discharged from the study. Subjects will report to the clinic in morning following a 10-hour fast. Subjects will complete the following evaluations:

- Review of prior and current medications and supplements;
- Physical examination;
- Measurement of weight;
- Measurement of vital signs (SBP/DBP and heart rate);
- Collection of fasted blood and urine samples for clinical safety labs for hematology, serum chemistry and urinalysis (see [Section 6.1.5.1](#) for list of tests);
- AEs/SAEs assessment;
- Discharge from CRU, if applicable.

Any subject with a possible study treatment related AE at the time of EW will be followed until resolution or stabilization of the event.

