### 6.2.2 Hemoglobin A1c (HbA1c)

Hemoglobin A1c will be collected at every visit.

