#### **8.4.2 Hemoglobin A1c (HbA1c)**

Hemoglobin A1c will be collected prior to dosing and after 28 days of dosing. This parameter will be analyzed using an Analysis of Covariance model with treatment as the main effect and baseline value as the covariate.

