### 8.5.8 Handling of Missing, Unused, or Spurious Data

Descriptive statistics and listings will be provided for all data. No substitution of missing data will be used in any calculations. Data points that appear to be spurious will be investigated and will not be excluded from the listings. Influential cases will be handled in an appropriate statistical manner.

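### The Day 14 HbA1c has no role in the between-arm comparison, so a subject who leaves after Visit 2 and before the Day 28 draw is lost to it despite having an on-treatment value

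*Combined protocol and SAP*

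**What the plan says.** - **Collection.** Section 3.3.2 (Visit 2, Day 14): "Blood sample will be collected to measure HbA1c". Section 6.2.2: "Hemoglobin A1c will be collected at every visit". Table 1 marks HbA1c at Screening and on Days 0, 14, 28 and 29, with no mark under Early Withdrawal.
- **Endpoint.** Section 2: "Mean changes in HbA1c from baseline to Day 29 of the treatment period".
- **Analysis.** Section 8.4.2: "Hemoglobin A1c will be collected prior to dosing and after 28 days of dosing". The model follows: "This parameter will be analyzed using an Analysis of Covariance model with treatment as the main effect and baseline value as the covariate". Day 14 is not named.
- **Missing data.** Section 8.5.8: "No substitution of missing data will be used in any calculations". The same section states: "Descriptive statistics and listings will be provided for all data".
- **Early withdrawal.** Section 3.6 lists "Collection of fasted blood and urine samples for clinical safety labs for hematology, serum chemistry and urinalysis". HbA1c is not among the procedures.
- **Further detail.** The opening of Section 8 defers additional detail to a statistical analysis plan, and no separate plan is in the supplied document.

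**The concern.** HbA1c is the only secondary efficacy laboratory measure that Table 1 schedules mid-treatment. For glucose, ketones and free fatty acids, and lipids, the sampling times in Section 6.2 match those in Section 8.4. For HbA1c, Section 6.2.2 refers to all visits, while Section 8.4.2 refers to two time points. The Day 14 value is collected but has no stated use in comparing the arms.

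This matters only for subjects who attend Visit 2 and leave before the Day 28 draw. The ANCOVA has no outcome for them, no value may be substituted, and the early-withdrawal visit does not supply one. The comparison is then a complete-case analysis. It loses some precision, and if leaving is related to glycaemia already visible at Day 14, and differs between the arms, it is also biased.

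**Working it through.** **Step 1: trace one subject.** Take a subject who attends Visit 2 and leaves before Day 28.

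- Baseline HbA1c is available (Screening and Visit 1, Table 1).
- Day 14 HbA1c is available (Section 3.3.2).
- Week 4 HbA1c is absent, and Section 3.6 draws none at early withdrawal.
- Substitution is excluded (Section 8.5.8).

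The subject cannot enter the Section 8.4.2 model. The Day 14 value appears only in the descriptive statistics and listings.

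**Step 2: inputs for the size.** The plan has no figure to reproduce. Section 8.2 says that the sample size had no statistical basis, and no dropout rate, SD or effect size is given. Section 5.2 gives about 40 subjects in two groups. Everything else here is assumed:

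- N = 20 per arm (the allocation ratio is not stated)
- m = fraction with a Day 14 value but no Week 4 value, 5 to 15%, equal in both arms
- ρ = correlation of the Day 14 and Week 4 changes given baseline, 0.5 to 0.8
- SD = 1

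**Step 3: precision.** With n = N(1 − m) completers per arm:

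- Complete-case variance of the Week 4 difference: 2/n
- Variance using Day 14: 2[(1 − ρ²)/n + ρ²/N]
- Ratio of the second to the first: 1 − mρ²
- Reduction in standard error: 1 − √(1 − mρ²)

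| m | ρ = 0.5 | ρ = 0.7 | ρ = 0.8 |
|---|---|---|---|
| 5% | 0.6% | 1.2% | 1.6% |
| 10% | 1.3% | 2.5% | 3.3% |
| 15% | 1.9% | 3.7% | 4.9% |

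For example, at m = 10% and ρ = 0.7 the ratio is 1 − 0.10 × 0.49 = 0.951, and √0.951 = 0.975. In relation to full data, the complete-case standard error is inflated by 1/√0.9 = 1.054; using Day 14 brings this to 1.054 × 0.975 = 1.028, so about half of the loss is recovered. The formula treats the covariance as known, so it slightly flatters the gain in a small trial.

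**Step 4: bias in a deliberately extreme case.** Suppose that the worst fraction q on Day 14 change leaves one arm, and nobody leaves the other arm for that reason. The mean Day 14 change of those who remain shifts by φ(z_q)/(1 − q) SD. The Week 4 mean shifts by ρ times that amount.

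- q = 10%: 0.195 × 0.7 = 0.14 SD
- q = 15%: 0.274 × 0.7 = 0.19 SD

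The full-data standard error of the difference is √(2/20) = 0.32 SD, so the shift is about 0.4 to 0.6 of a standard error. It comes from two or three subjects (10 to 15% of 20). A correctly specified repeated-measures model removes it when leaving depends only on observed values.

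**Step 5: no dropout.** With m = 0 the ratio is 1, and the Week 4 estimate is essentially the same under both models.

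**The case against.** The case for leaving the plan alone is reasonable.

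- **The ANCOVA fits the endpoint.** The endpoint is change to the end of treatment, and drawing an interim sample does not oblige the sponsor to model it. A reader might infer that the ANCOVA is wrong. It is not: it is valid with complete data, and the argument here is for a cheap improvement.
- **The value is not ignored.** A reader might infer that the Day 14 result enters no analysis at all. Section 8.5.8 promises descriptive statistics and listings for all data, so the gap is confined to the between-arm comparison.
- **The window is narrow.** HbA1c is drawn on the morning of Day 28 and again on Day 29. A subject admitted for Visit 3 has a Week 4 value even if the infusion fails, provided that the Day 28 value counts.
- **Informative dropout is not shown.** A reader might infer that the HbA1c comparison is biased. The documents give no dropout rate, and Section 4.3 has no HbA1c withdrawal criterion. It does list unresponsive hypoglycaemia and use of prohibited medication, so leaving related to glycaemia is possible, but the one-sided case in the working is an extreme.
- **Withdrawn subjects may be replaced** (Section 4.3). That can restore numbers and so offset the loss of precision. It does not correct selective leaving.
- **The analysis plan may deal with it.** That text is not supplied, so it cannot be assumed to do so.

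These points limit the size of the concern. They do not give the Day 14 value a role in the comparison.

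**Conclusion.** The point holds as a minor one. As Section 8.4.2 stands, a subject who attends Visit 2 and leaves before the Day 28 draw is absent from the HbA1c comparison despite having an on-treatment value. This follows from combining the ANCOVA, the no-substitution rule and the early-withdrawal procedures; the protocol does not state it outright, and it defines no efficacy population.

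Under assumed losses of 5 to 15% and a correlation of 0.5 to 0.8, using the value lowers the standard error by about 1 to 5%. Protection against bias applies only where leaving depends on observed values. HbA1c is a secondary endpoint, and the primary tracer AUC is untouched.

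**What to change.** In Section 8.4.2, or in the analysis plan before unblinding:

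1. Analyse change from baseline in HbA1c at Day 14 and Week 4 with a mixed model for repeated measures: treatment, visit, treatment-by-visit, baseline, baseline-by-visit, and unstructured covariance.
2. Take the Week 4 treatment contrast as the endpoint.
3. Name the single baseline value (Screening or Visit 1) and the single Week 4 value (Day 28 or Day 29; the endpoint says Day 29). The model is undefined until this is settled.
4. State that all observed values at the two visits are used and none is imputed, which keeps to Section 8.5.8. Carrying Day 14 forward would not be equivalent, because it is not a 4-week value.
5. Keep the Week 4 ANCOVA as a sensitivity analysis.

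The cost is a paragraph of text and a little programming, since the blood is already drawn. The small downside is one extra covariance structure to estimate with about 40 subjects.

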### 3.4 Tracer Infusion

#### 3.4.1 Visit 3 (Week 4, Day 28)

Subjects will report to the clinic in morning following a 10-hour fast. At Visit 3 (Day 28), the following procedures will be performed:

- Admission to the CRU (8 AM  $\pm$  120 minutes);
- Review of prior and current medications and supplements;
- Measurement of vital signs (SBP/DBP and heart rate);
- Measurement of weight;
- Breathalyzer;
- Urine pregnancy test (women of childbearing potential/WCBP only);
- Fasting blood sample will be collected to measure HbA1c;
- Study medication will be collected, and compliance will be reviewed;
- Subjects will be provided with a standard breakfast, lunch and dinner. The morning dose will be administered 45 minutes ( $\pm$  15 minutes) before breakfast and no later than 10 AM, in-clinic. A light standardized dinner meal will be provided at 6 PM  $\pm$  30 minutes.
- Subjects will be dosed in-clinic with either ORMD-0801 (8 mg) or placebo (@ 8 PM  $\pm$  60 minutes) and started on a 16-hour infusion of [6,6-H2]-glucose tracer immediately following dosing;
- Blood samples will be collected to measure endogenous glucose (tracer attached), plasma glucose, metabolites and hormones for the duration of the infusion. Blood samples will be drawn at baseline (pre-infusion), 45, 90, 120 and 150 minutes, and 3 and 4 hours (see blood draw schedule in [Table 2](#)). Subjects will be required to remain fasting from the evening of Day 28 (following dinner) until the end of the infusion;
- A backup blood sample will be collected at baseline (pre-infusion);
- AEs/SAEs assessment.

### 3.5 Discharge/End of Study

#### 3.5.1 Visit 3 (Week 4, Day 29)

At Visit 3 (Day 29), the following procedures will be performed:

- Review of prior and current medications and supplements;
- Physical examination;
- Measurement of vital signs (SBP/DBP and heart rate);
- Fasting blood sample will be collected to measure HbA1c;
- Collection of fasted blood and urine samples for clinical safety labs for hematology, serum chemistry and urinalysis (see [Section 6.1.5.1](#) for list of tests);
- Blood samples will be collected to measure endogenous glucose (tracer attached), plasma glucose, metabolites and hormones for the duration of the infusion. Blood samples will be drawn at 5, 6, 7, 8, 9, 10, 11, 12, 13, 14, 15 and 16 hours (see blood draw schedule in [Table 2](#)). Subjects will be required to remain fasting from the evening of Day 28 (following dinner) until the end of the infusion;

- A backup blood sample will be collected 16-hour after infusion;
- After completion of the infusion, subjects will be provided with a standard lunch;
- AEs/SAEs assessment;
- Following the 6-hour observation and end of study procedures, subjects will be discharged from the CRU in the evening.

### **3.6 Early Withdrawal (EW)**

If a randomized subject is withdrawn from the study prior to completion, the subject will be instructed to return to the clinic the next day and will have the early term (ET) visit procedures completed. Subjects will then be discharged from the study. Subjects will report to the clinic in morning following a 10-hour fast. Subjects will complete the following evaluations:

- Review of prior and current medications and supplements;
- Physical examination;
- Measurement of weight;
- Measurement of vital signs (SBP/DBP and heart rate);
- Collection of fasted blood and urine samples for clinical safety labs for hematology, serum chemistry and urinalysis (see [Section 6.1.5.1](#) for list of tests);
- AEs/SAEs assessment;
- Discharge from CRU, if applicable.

Any subject with a possible study treatment related AE at the time of EW will be followed until resolution or stabilization of the event.

### **3.7 Schedule of Events**

[Table 1](#) below describes the daily schedule of events from Screening (Visit 0) to Discharge/End of Study (Visit 3, Day 29).

**Table 1: Schedule of Events from Screening (Visit 0) to Discharge/End of Study (Visit 3, Day 29).**

	Screening	Treatment Period			Discharge / End of Study	Early Withdrawal
				TRACER Infusion		
Visit	0	1	2	3		
Week	-3 to -1	0	2		4	
Day	-21 to -7	0	14	28	29	
Informed Consent	X					
Inclusion/Exclusion	X	X				
Demographics (sex, age, race and ethnicity)	X					
Medical and Social History (including tobacco, alcohol, caffeine and drug use)	X					
Prior/Concomitant Medications	X	X	X	X	X	X
Physical Examination	X				X	X
12-lead ECG	X					
Height, Weight, BMI	X	X	X	X		X
Vital Signs	X	X	X	X	X	X
Chemistry, Hematology, Urinalysis	X				X 	X
Blood Collection for Plasma Glucose, Metabolites and Hormones	X			X	X	
Urine Drug Screen	X					
Serum Pregnancy Test	X					
Urine Pregnancy Test				X		
Breathalyzer	X	X	X	X	X	

	Screening	Treatment Period			Discharge / End of Study	Early Withdrawal
				TRACER Infusion		
Visit	0	1	2		3	
Week	-3 to -1	0	2		4	
Day	-21 to -7	0	14	28	29	
HbA1c	X	X	X	X	X	
Randomization		X				
Dispense study medication		X	X			
Collect study medication and review for compliance			X	X		
CRU Admission				X		
In-Clinic Dosing				X		
TRACER Infusion				X	X	
Blood Collection for Tracer Marked Glucose, Metabolites and Hormones				X	X	
Standard Meals				X	X	
CRU Discharge					X 	X
Adverse Events		X	X	X	X	X
End of Study					X	X

 Weight will be measured at each visit. Height will be measured and BMI will be calculated at Screening.

 Blood draw will be performed after the 16-hour infusion is complete.

 A blood plasma sample will be collected at Screening and during infusion for assessment of plasma glucose, metabolites and hormones according to [Table 2](#).

 Serum pregnancy test and urine pregnancy test will be performed for women of childbearing potential (WCBP) only.

 Subjects will be started on a 16-hour infusion of TRACER immediately following dosing. Refer to [Appendix A](#) (Guidelines for TRACER Infusion).

 Blood samples will be collected during the duration of infusion based on the blood draw schedule in [Table 2](#).

 A standard breakfast, lunch, and dinner will be provided on Day 28. Subjects will fast following dinner on Day 28 until the completion of the 16-hour infusion on Day 29. After completion of the infusion, subjects will be provided with a standard lunch.

 Following the 6-hour observation and end of study procedures, subjects will be discharged from the CRU in the evening of Day 29.

**Table 2: Blood Draw Schedule**

additive	EDTA+NaF	EDTA	EDTA	EDTA+30 µL diprotin+20 µL Foy°	EDTA+30 µL diprotin+20 µL Foy°	
assay	Tracer	Glucose	Metabolites#	Hormones§	Backup	total
Time	mL	mL	mL	mL	mL	mL
Baseline*	2	1	3	3	4	13
45 min	2	1	3	3		9
90 min	2	1	3	3		9
120 min	2	1	3	3		9
150 min	2	1	3	3		9
3 hours	2	1	3	3		9
4 hours	2	1	3	3		9
5 hours	2	1	3	3		9
6 hours	2	1	3	3		9
7 hours	2	1	3	3		9
8 hours	2	1	3	3		9
9 hours	2	1	3	3		9
10 hours	2	1	3	3		9
11 hours	2	1	3	3		9
12 hours	2	1	3	3		9
13 hours	2	1	3	3		9
14 hours	2	1	3	3		9
15 hours	2	1	3	3		9
16 hours	2	1	3	3	4	13
Total	38	19	57	57	8	179

\* before starting tracer infusion

° Foy master solution = 0.035 mg in 10 mL of saline

#  $\beta$ -hydroxybutyrate, acetoacetate, lactate, pyruvate, FFA, glycerol

§ insulin, C-peptide, glucagon

## 4 STUDY SUBJECT SELECTION

### 4.1 Inclusion Criteria

1. Male and female subjects aged, 18 - 70 years.
2. Established diagnosis of T2DM for at least 6 months prior to Screening, with HbA1c  $\geq 7.5\%$ . and  $\leq 11\%$ .
3. Stable dose of metformin (at least 1500 mg or maximal tolerated dose) for a period of at least 3 months prior to Screening.
4. Taking metformin only or metformin in addition to no more than two of the following: DPP-4, SGLT-2, or TZD.
5. Body mass index (BMI) of up to  $35 \text{ kg/m}^2$  at Screening and stable weight, with no more than 5 kg gain or loss in the 3 months prior to Screening.
6. Renal function – eGFR  $> 30 \text{ ml/min/1.73 m}^2$ .
7. Females of childbearing potential must have a negative serum pregnancy test result at Screening.
  - a. Females who are not of childbearing potential are defined as:
    - i. Postmenopausal (defined as at least 12 months with no menses in women  $\geq 45$  years of age);
    - ii. Has had a hysterectomy and/or bilateral oophorectomy, bilateral salpingectomy, or bilateral tubal ligation/occlusion at least 6 weeks prior to screening; OR
    - iii. Has a congenital or acquired condition that prevents childbearing.
  - b. Females of childbearing potential agree to avoid becoming pregnant while receiving study treatment and for 14 days after the last dose of study treatment by complying with one of the following:
    - i. Practice abstinence† from heterosexual activity; OR
    - ii. Use (or have her partner use) acceptable contraception during heterosexual activity. Acceptable methods of contraception are‡:
      1. Single method (one of the following is acceptable):
        - a. Non-hormonal intrauterine device (IUD);
        - b. vasectomy of a female subject's male partner.
      2. Combination method (requires use of two of the following):
        - a. diaphragm with spermicide (cannot be used in conjunction with cervical cap/spermicide);
        - b. cervical cap with spermicide (nulliparous women only);
        - c. contraceptive sponge (nulliparous women only);
        - d. male condom or female condom (cannot be used together).

†Abstinence (relative to heterosexual activity) can be used as the sole method of contraception if it is consistently employed as the subject's preferred and usual lifestyle and if considered acceptable

by local regulatory agencies and ERCs/IRBs. Periodic abstinence (e.g., calendar, ovulation, symptothermal, post-ovulation methods, etc.) and withdrawal are not acceptable methods of contraception.

If a contraceptive method listed above is restricted by local regulations/guidelines, then it does not qualify as an acceptable method of contraception for subjects participating at sites in this country/region.

